1 st occurrence and subsequent occurrences	
 Educate patient about pyrexia syndrome and to immediately interrupt dabrafenib and trametinib at the very first symptom of pyrexia or its associated prodrome (chills or rigors or night sweats or flu-like symptoms). Clinical evaluation for infection and hypersensitivity ^a Laboratory work-up ^a Administer anti-pyretic treatment 	
 Dabrafenib and trametinib must be interrupted promptly at the very first symptom of pyrexia or its associated prodrome (chills, rigors, night sweats or flu-like symptoms) and should be restarted upon improvement of symptoms at the same dose if symptom free at least 24 hours. If pyrexia cannot be managed with interruption, dose reduction per Table 6-7 must be considered if clinically indicated. For re-

Pyrexia		
Occurrence	Recommended adverse event management guidelines	Mandatory dose modification requirements
	with non-steroidal anti-inflammatory drugs (NSAID) and/or paracetamol ^b 
 • Recommend oral corticosteroids (i.e., prednisone 10 mg) for at least 5 days or as clinically indicated. • Optimize oral corticosteroid dose as clinically indicated for recalcitrant pyrexia. • Oral hydration should be encouraged in subjects without evidence of dehydration. Intravenous hydration is recommended in subjects experiencing pyrexia complicated by dehydration/hypotension. 	escalation, refer to Section 6.3.2 . 
 • Note: proactive intermittent dosing is not allowed.

^a. For subjects experiencing pyrexia, a clinical evaluation and laboratory work-up is mandatory for each event; thorough clinical examination for signs and symptoms of infection or hypersensitivity is required; laboratory work-up should include full-blood-count, electrolytes, creatinine, blood urea nitrogen (BUN), C-reactive protein (CRP), liver-function tests, blood culture, and urine culture.
 
^b. Anti-pyretic treatment should be started immediately at the first occurrence and prophylactic anti-pyretic treatment is recommended. Anti-pyretic treatment may include acetaminophen, ibuprofen, or suitable anti-pyretic medication according to institutional standards. Prophylactic anti-pyretic treatment is recommended to be discontinued after three days in the absence of pyrexia.
		

6.3.5.5 Mandatory dose modification and management guideline for visual changes suspected to be related to dabrafenib and/or trametinib treatment

Episodes of visual changes have been observed in subjects receiving trametinib, dabrafenib or the combination of dabrafenib/trametinib. An ophthalmologist should be consulted if changes in vision develop. However, if the visual changes are clearly unrelated to study treatment (e.g., allergic conjunctivitis), then monitor closely as it may be reasonable to defer ophthalmic examination.

Treatment with dabrafenib has been associated with the development of uveitis, including iritis. Monitor subjects for visual signs and symptoms (such as, change in vision, photophobia and eye pain) during therapy. Permanently discontinue dabrafenib for persistent \geq Grade 2 uveitis (including iritis and iridocyclitis) of $>$ 6 weeks duration. No dose modification of trametinib is required when taken in combination with dabrafenib.

In subjects treated with trametinib, special attention should be given to retinal findings (e.g., RPED) or retinovascular abnormalities (i.e., branch or central RVO). Treatment emergent cases of RVO and RPED should be reported as SAEs.

Guidelines for dose modification and management for visual changes and/or ophthalmic examination findings considered to be related to dabrafenib and/or trametinib are provided in [Table 6-25](#) and [Table 6-26](#).

[figure not shown]

Table 6-25 Mandatory dose modification and recommended clinical management for visual changes and/or ophthalmic examination findings suspected to be related to dabrafenib and/or trametinib treatment

Visual changes (Eye disorders – Other, CTCAE Version 4.03)		
Grade	Recommended adverse event management guidelines	Mandatory dose modification requirements
Grade 1 ^a	
 Consult ophthalmologist within 7 days of onset 	
 If dilated fundus examination cannot be performed within 7 days of onset, interrupt trametinib until RPED and RVO can be excluded by retina specialist/ophthalmologist. Continue dabrafenib. If RPED and RVO excluded, continue (or restart) trametinib at the same dose level. If RPED suspected or diagnosed: see RPED dose modification in Table 6-26; report as SAE if diagnosed. If RVO diagnosed: Permanently discontinue trametinib and report as SAE.
Grade 2 and Grade 3	
 Consult ophthalmologist immediately 	
 Interrupt trametinib. Dabrafenib may be continued at the same dose ^b. If RPED and RVO excluded, restart trametinib at the same dose level. If RPED diagnosed, see RPED dose modification in Table 6-26; report as SAE. If RVO diagnosed: Permanently discontinue trametinib and report as SAE.
Grade 4	
 Consult ophthalmologist immediately 	
 Interrupt trametinib. Dabrafenib may be continued at the same dose ^b. If RPED and RVO excluded, should consider restarting trametinib at same or reduced dose after discussion with study medical monitor. If RVO or RPED diagnosed, permanently discontinue trametinib and report as SAE.

^a. If visual changes are clearly unrelated to study treatment (e.g., allergic conjunctivitis), monitor closely but ophthalmic examination is not required.

^b. Permanently discontinue dabrafenib for ≥ Grade 2 uveitis (including iritis and iridocyclitis) of > 6 weeks duration.

Table 6-26 Mandatory dose modification and recommended clinical management for retinal pigment epithelial detachments (RPED) suspected to be related to trametinib treatment

Retinal pigment epithelial detachments (RPED)		
Grade	Recommended adverse event management guidelines	Mandatory dose modification requirements

 Grade 1 (Asymptomatic; clinical or diagnostic observations only) 	
 If RPED worsens follow instructions below. 	
 Continue treatment with retinal evaluation monthly until resolution.

 Grade 2-3 RPED (Symptomatic with mild to moderate decrease in visual acuity). 	
 Retinal evaluation monthly. 	
 Interrupt trametinib. If improved to ≤ Grade 1, restart trametinib at a lower dose per Table 6-7.

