6.3.1 General dose modification instructions for PDR001 or placebo

No dose reductions are allowed for PDR001. Dose interruption for PDR001/placebo includes delaying or withholding the treatment for any reason as well as an interruption of treatment during an infusion. Subjects with adverse events suspected to be related to PDR001 or placebo including those of potential immune-mediated etiology (irAE) (see definition in [Section 6.3](#)) must be permanently discontinued from PDR001 or placebo if (1) the AE doesn't recover to ≤ Grade 1 or baseline within 12 weeks and/or (2) the dose of steroids (for the management of irAE) remains > 10 mg/day prednisone or equivalent for >12 weeks.

The 12 week timeframe will begin from the time the irAE reaches a grade that leads to PDR001/placebo interruption.

Subjects who discontinue the study for a study related adverse event or an abnormal laboratory value must be followed as described in [Section 7](#).

6.3.2 General dose modification instructions for dabrafenib and trametinib:

[figure not shown]
If treatment related toxicities occur that are specific to combination treatment of dabrafenib and trametinib, then both treatments should be simultaneously dose reduced, interrupted or discontinued with the exceptions shown below:

Exception where dose modification is necessary for **only dabrafenib**:

- Uveitis ([Table 6-25](#))

Exception where dose modifications are necessary for **only trametinib**:

- Retinal vein occlusions (RVO) ([Table 6-25](#)) and retinal pigment epithelial detachment (RPED) ([Table 6-26](#))
- Left ventricular ejection fraction (LVEF) reduction ([Table 6-22](#))

If a subject’s dose of dabrafenib and trametinib has been reduced per the dose modification instructions, re-escalation of the subject’s dose is recommended provided the following criteria are met:

- a period of 4 weeks of treatment has passed since restarting dosing at the lower dose level and there is no recurrence of the AE
- the subject is deriving clinical benefit

For dabrafenib and/or trametinib related adverse events: if following an interruption of dabrafenib and trametinib, an AE doesn’t recover to ≤ Grade 1 or baseline within 4 weeks, dabrafenib and trametinib must be discontinued.

6.3.3 Dose modification and management guideline for adverse events common to PDR001, dabrafenib and trametinib

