
Grade 3 diarrhea (increase of ≥ 7 stools per day over baseline; incontinence; hospitalization indicated; severe increase in ostomy output compared to baseline; limiting self-care ADL) OR Grade 3 colitis (severe abdominal pain; change in bowel habits; medical intervention indicated; peritoneal signs)
	
 • Clinical evaluation and hospitalization mandatory; rule out bowel perforation and intravenous hydration. • Consider consultation with gastroenterologist and confirmation biopsy with lower GI endoscopy. • In addition to symptomatic treatment (diet, hydration, loperamide, antibiotics if indicated); initiate immediate treatment with intravenous steroids (methylprednisolone 1mg/kg/day) followed by high dose oral steroids (1 to 2 mg/kg/day prednisone equivalents) • When symptoms improve to \leq Grade 1, steroid taper should be started and continued over no less than 4 weeks as per Section 6.3.4.1. • Taper over 6 to 8 weeks in subjects with diffuse and severe ulceration and/or bleeding. • If no improvement in 2-3 days: consider initiating infliximab 5 mg/kg and continue steroids. 	
1st occurrence
 
 • Interrupt PDR001/placebo, dabrafenib and trametinib until \leq Grade 1, and then reinstate PDR001 treatment (after appropriate steroid tapering) and reduce dabrafenib and trametinib to the next lower dose level per Table 6-7. Re-escalation of the subject's dose is recommended if criteria in Section 6.3.2 are met. • AE resolution to \leq Grade 1 or baseline must occur within a period of 12 weeks since a grade 3 event has been identified, otherwise PDR001 must be permanently discontinued. 
2nd occurrence
 
 • Permanently discontinue PDR001/placebo. • Interrupt dabrafenib and trametinib until \leq Grade 1, and then reduce dabrafenib and trametinib to the next lower dose per Table 6-7. Re-escalation of the subject's dose is recommended if criteria in Section 6.3.2 are met. 
3rd occurrence

CTCAE v4.03	Recommended adverse event management guidelines	Mandatory dose modification requirements

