	
(Infliximab is contraindicated in subjects with sepsis or a perforation). Upon symptomatic relief initiate a prolonged steroid taper over 45 to 60 days.
 
 If symptoms worsen during steroid reduction, initiate a re-tapering of steroids starting at a higher dose followed by a more prolonged taper and administer infliximab. If symptoms persist despite the above treatment, a surgical consult should be obtained. 	
 Permanently discontinue dabrafenib and trametinib.
Grade 4: Life-threatening consequences; urgent intervention indicated	
 Same as Grade 3 	
 Permanently discontinue PDR001/placebo, dabrafenib and trametinib.

6.3.3.2 Mandatory dose modifications and recommended clinical management guidelines for abnormal liver enzyme test

Guidelines for dose modification and management of abnormal liver enzyme functions considered to be related to study treatment by the investigator are provided in [Table 6-10](#).

In addition to the instructions below, subjects with normal baseline transaminases and bilirubin who experience sudden elevations even within Grade 1, should be monitored more closely.

Table 6-10 Mandatory dose modifications and recommended clinical management guidelines for abnormal liver enzyme test

Abnormal liver enzyme tests/hepatitis		
Grade	Recommended adverse event management guidelines	Mandatory dose modification requirements
Grade 2: AST or ALT >3× ULN to ≤ 5× ULN and/or bilirubin > 1.5× ULN to ≤ 3× ULN	
 Monitor hepatic laboratory tests more frequently (every 2-3 days) until returned to baseline values 	
 Interrupt PDR001/placebo, dabrafenib and trametinib until ≤ Grade 1, and then reinstate PDR001/placebo, dabrafenib and trametinib at the same dose level.

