6.3.4.1 Guidance for corticosteroids tapering for management of immune-related AEs

Reduce prednisone dose by 2.5 to 5.0 mg decrements every 3–7 days until physiologic dose (5 to 7.5 mg of prednisone per day) is reached. Consider to complete tapering over a period of at least 4 weeks. Slower tapering of corticosteroids therapy may be recommended if the adverse event is not showing improvement. Once corticosteroid tapering is achieved at a level of ≤ 10 mg of prednisone/day (or equivalent), PDR001 can be restarted as indicated in the dose modification tables.

6.3.5 Dose modification and management guideline for adverse events suspected to be related to dabrafenib and/or trametinib

Continue PRD001/placebo.

For adverse events of special interest reported **only for dabrafenib and/or trametinib**, general guidelines for dose modification in [Table 6-21](#) should be followed for dabrafenib and trametinib.

In general, if an AE resolves to Grade 1 or baseline at the reduced dose level, and no additional toxicities are seen after 4 weeks of study treatment at the reduced dose, the dose may be increased to the previous dose level.

A dose reduction below 50 mg BID for dabrafenib or below 1 mg QD for trametinib is not allowed. If a dose reduction below 50 mg BID for dabrafenib is required, dabrafenib will be permanently discontinued but these subjects will be allowed to continue trametinib. If a dose reduction below 1.0 mg QD for trametinib is required, then trametinib will be permanently discontinued, but these subjects will be allowed to continue dabrafenib.

[figure not shown]

Table 6-21 General guidelines for dose modification for adverse events suspected to be related to dabrafenib and/or trametinib treatment

Grade	Recommended adverse event management guidelines	Mandatory dose modification requirements
Grade 1 or Grade 2 tolerable	
 Monitor closely. Provide supportive care according to institutional standards. 	
 Continue dabrafenib and trametinib at the same dose level.

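### At the upper end of the recommended steroid doses, the taper steps in Section 6.3.4.1 cannot meet the mandatory 12-week limit in Section 6.3.1 or the taper lengths in Table 6-9

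*Protocol*

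**What the plan says.** Section 6.3.4.1 sets the taper: "Reduce prednisone dose by 2.5 to 5.0 mg decrements every 3–7 days until physiologic dose". It adds "Consider to complete tapering over a period of at least 4 weeks", and the only departure from the steps that it mentions is a slower taper when the event is not improving. It then states: "Once corticosteroid tapering is achieved at a level of ≤ 10 mg of prednisone/day (or equivalent), PDR001 can be restarted". Section 6.4.3.1 makes the 10 mg/day level a condition for the next administration of study treatment.

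Section 6.3.1 requires permanent discontinuation of PDR001 or placebo if the event does not recover within 12 weeks, and/or if "the dose of steroids (for the management of irAE) remains > 10 mg/day prednisone or equivalent for >12 weeks". The 12 weeks run from the time the event reaches the grade that leads to interruption.

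For Grade 3 diarrhea/colitis, Table 6-9 (Section 6.3.3.1) recommends oral steroids at 1 to 2 mg/kg/day. Tapering starts only once symptoms are Grade 1 or less, lasts at least 4 weeks, and is referred to Section 6.3.4.1. The same row also says "Taper over 6 to 8 weeks in subjects with diffuse and severe ulceration and/or bleeding" and, after infliximab, "initiate a prolonged steroid taper over 45 to 60 days". At a first occurrence PDR001 is to be reinstated after tapering.

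The 1 to 2 mg/kg range together with a first-occurrence restart also appears for Grade 3 rash (Table 6-11), Grade 3 renal events (Table 6-12), Grade 2 pneumonitis (Table 6-13), symptomatic endocrinopathy (Table 6-15) and Grade 3 events in Table 6-19.

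**The concern.** The starting dose scales with body weight, while the taper step is a fixed number of milligrams. The time needed to reach 10 mg/day therefore grows with weight and dose, but the 12-week limit and the Table 6-9 durations do not. If the permitted steps take longer than the limit, two instructions collide: the table says to reinstate PDR001, and Section 6.3.1 says to stop it for good. The subject concerned has recovered from the event and is still above 10 mg/day only because of the prescribed pace. Consistent handling of PDR001 after immune-related events, across sites and subjects, is what is at stake.

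**Working it through.** The 12-week limit is a fixed rule with no derivation to reproduce, so the check is whether the taper fits inside it.

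**Inputs**
- Step d = 2.5 to 5.0 mg, interval k = 3 to 7 days, restart level 10 mg/day (Section 6.3.4.1).
- Limit 12 weeks = 84 days, counted from the interrupting grade (Section 6.3.1).
- Starting dose S = 1 to 2 mg/kg/day; tapers of 6 to 8 weeks (42 to 56 days) and 45 to 60 days (Table 6-9).
- Weight range 30 to 150 kg (Section 1.2.1.2). Individual weights below are examples.
- Days before tapering starts: not given; 0, 14 and 28 are assumed.

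**Formulas**
- Days to reach 10 mg = ceil((S − 10)/d) × k, with the first reduction after one interval.
- Largest S that fits T days = 10 + d × floor(T/k).

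**Examples, days to 10 mg**
- 70 kg at 1 mg/kg (70 mg): 60/5 = 12 steps. At 3 days, 36 days (5.1 weeks); at 7 days, 84 days (exactly 12.0 weeks). With 2.5 mg steps, 24 steps: 72 days, or 168 days (24 weeks).
- 70 kg at 2 mg/kg (140 mg): 130/5 = 26 steps. At 3 days, 78 days (11.1 weeks); at 7 days, 182 days (26 weeks). With 2.5 mg weekly, 52 × 7 = 364 days (52 weeks).
- 80 kg at 2 mg/kg (160 mg): 150/5 = 30 steps. At 3 days, 90 days (12.9 weeks), already past the limit at the fastest rate.

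**Largest starting dose that reaches 10 mg within the 84 days**

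| Rate | No delay | 14 days' delay | 28 days' delay |
|---|---|---|---|
| 5 mg / 3 days | 10 + 5 × 28 = 150 mg | 125 mg | 100 mg |
| 2.5 mg / 3 days | 10 + 2.5 × 28 = 80 mg | 67.5 mg | 55 mg |
| 5 mg / 7 days | 10 + 5 × 12 = 70 mg | 60 mg | 50 mg |
| 2.5 mg / 7 days | 10 + 2.5 × 12 = 40 mg | 35 mg | 30 mg |

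Dividing the first row by 2 mg/kg gives the weights above which no permitted rate works: 75, 62.5 and 50 kg. Dividing by 1 mg/kg gives 150, 125 and 100 kg.

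**Table 6-9 tapers at the fastest rate, from the start of tapering**
- 6 weeks: 10 + 5 × 14 = 80 mg, or 40 kg at 2 mg/kg.
- 8 weeks: 10 + 5 × 18 = 100 mg, or 50 kg at 2 mg/kg and 100 kg at 1 mg/kg.
- 45 days: 10 + 5 × 15 = 85 mg, or 42.5 kg at 2 mg/kg.
- 60 days: 10 + 5 × 20 = 110 mg, or 55 kg at 2 mg/kg.

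For 70 kg at 2 mg/kg, the fastest permitted taper (78 days to 10 mg) is longer than the taper that Table 6-9 itself calls prolonged.

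**Sensitivity.** Making the first reduction on day 0 raises each no-delay limit by one step (150 to 155 mg, that is 77.5 kg at 2 mg/kg). Tapering on to the physiologic dose of 5 to 7.5 mg, rather than 10 mg, lowers the 8-week limit from 100 mg to 95–97.5 mg.

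**The case against.** The strongest reply is that the taper is guidance. Section 6.3.4.1 is headed as such, steroid doses sit in the tables' recommended-management column, and the 12-week stop is mandatory. An investigator can choose a lower starting dose or the faster steps, and over much of the range that suffices. This stands, and it rules out the reading that the taper can never be completed in time. It does not remove the conflict: the Grade 3 colitis row sends the taper to Section 6.3.4.1, that section offers nothing faster than 5 mg every 3 days, and a starting dose above 150 mg fails at every permitted rate although 2 mg/kg is within the recommendation.

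A second reply is that the 6 to 8 week and 45 to 60 day tapers are colitis-specific and displace the general steps. That is a possible reading, since those two sentences do not cite Section 6.3.4.1. But the protocol does not say so, and an earlier sentence in the same row does cite it.

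A third is that stopping PDR001 when steroids cannot be brought down is the purpose of Section 6.3.1. That is right for subjects whose event is not improving. It does not cover subjects who have recovered and are held above 10 mg/day only by the step size.

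A reader might go further and infer that many first-occurrence events become permanent stops, or that the tested effect was diluted through lost exposure in one arm. The protocol gives no count of steroid-treated events, their doses or their tapers. Some rows require permanent discontinuation anyway, such as Grade 3 pneumonitis and Grade 3 or 4 encephalitis. The reported 36.3% versus 17.8% for adverse events leading to discontinuation of any drug isolates neither PDR001, nor immune events, nor this rule, so it is not evidence here.

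**Conclusion.** The provisions are wrong as written over part of the recommended dose range. With no delay before tapering, 2 mg/kg exceeds the 12-week limit at every permitted rate above 75 kg; slower steps exceed it from starting doses above 80, 70 or 40 mg, depending on the rate. At 2 mg/kg an 8-week taper is out of reach above 50 kg and a 60-day taper above 55 kg. At 1 mg/kg the fastest steps fit 12 weeks to 150 kg and 8 weeks to 100 kg, so the conflict is partial.

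The no-delay thresholds follow from the protocol's own figures. The lower thresholds (62.5 and 50 kg) rest on the assumed 14 and 28 days to improvement. The number of subjects affected is unknown. The final PFS analysis is complete (cut-off 01-Jul-2020), so what remains is consistent handling of subjects still on PDR001. Amendment 7 lists 2 subjects on treatment in part 1, one in part 2 and 88 in part 3, the last without a split by arm.

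**What to change.** Reconcile Section 6.3.1, Section 6.3.4.1 and the Grade 3 row of Table 6-9 so that a subject started anywhere in the recommended steroid range can satisfy all of them, or state which provision governs when they conflict. Say explicitly whether the Table 6-9 durations replace the general steps, and check the other tables that pair 1 to 2 mg/kg with a PDR001 restart. Inform sites still treating subjects with PDR001. The clinical team decides the schedule; no dose, step or time limit is proposed here. The cost is protocol wording and an investigator letter.

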recorded on the Dosage Administration Record eCRF. Three dose reductions for dabrafenib and two dose reductions for trametinib are permitted. If more dose reductions of dabrafenib and trametinib are required, the subject must be permanently discontinued from that specific study treatment. Dose modification steps for PDR001 or placebo, dabrafenib and trametinib in [Table 6-7](#) must be followed for the AEs presented in [Section 6.3](#).

[Table 6-8](#) provides a list of AEs of special interest and relevant sections where detailed dose modification and management requirements for relevant AEs and/or irAEs can be found. All AEs are to be graded according to NCI-CTCAE v4.03, unless otherwise specified. Investigators should refer to the current PDR001 Investigator's Brochure and the dabrafenib and trametinib local prescribing information for additional information regarding the background of each drug and the management of other AEs or potential safety-related issues not specifically mentioned in this protocol.

Trial participants with confirmed active COVID-19 infection or presenting with symptoms indicative of COVID-19 infection which may include but not limited to fever, cough, difficulty breathing, sore throat, pneumonia, loss of sense of smell, or taste or feeling unwell with flu like symptoms may interrupt study treatment based on the risk benefit assessment; in case of suspected COVID-19 infection, testing for COVID-19 is recommended as per local guidelines.

Should a patient require treatment for COVID-19 infection, the investigator should assess the risks and benefits of continued study drug treatment during this time. The investigator may consider holding study treatment until the patient is stable to restart because of potential drug to drug interaction. Additionally, the concomitant medications are to be documented in the relevant eCRF.

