General		X	X	Section 6.3.5 Table 6-21

Adverse Events	PDR001	dabrafenib	trametinib	Guideline
LVEF		X	X	Section 6.3.5.1 Table 6-22
Hypertension		X	X	Section 6.3.5.2 Table 6-23
New malignancies		X	X	Section 6.3.5.3.
Pyrexia syndrome		X	X	Section 6.3.5.4 Table 6-24
Visual changes		X (Uveitis)	X (RVO)	Section 6.3.5.5 Table 6-25
RPED			X	Section 6.3.5.5 Table 6-26
Hyperglycemia		X		Section 6.3.5.6
Hemorrhage		X	X	Section 6.3.5.7
Thromboembolic events			X	Section 6.3.5.8
Hemophagocytic lymphohistiocytosis		X	X	Section 6.3.5.9
"X" indicates study treatment (s) that may need to be modified.				

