
Asymptomatic: Absolute decrease of >10% in LVEF compared to baseline and ejection fraction below the institution's LLN
	
 Report as SAE. Closely monitoring LVEF via ECHO, repeat ECHO within 2 weeks*. If the LVEF recovers within 4 weeks (defined as LVEF \geqLLN and absolute decrease \leq10% compared to baseline) 
 Repeat ECHO 2, 4, 8 and 12 weeks after re-start; continue in intervals of 12 weeks thereafter. If repeat LVEF does not recover within 4 weeks. 
 Consult with cardiologist Repeat ECHO after 2, 4, 8, 12, and 16 weeks or until resolution 	
 Interrupt trametinib. If the LVEF recovers, restart trametinib reduced by one dose level per Table 6-7 and continue dabrafenib at the same dose level. More than two occurrence, permanently discontinue trametinib. Permanently discontinue trametinib if repeat LVEF does not recover within 4 weeks.

Symptomatic: Resting LVEF 39-20% or >20% absolute reduction from baseline resting LVEF <20%
	
 Report as SAE. Consult with cardiologist. Repeat ECHO after 2, 4, 8, 12, and 16 weeks or until resolution. 	
 Permanently discontinue trametinib. Interrupt dabrafenib Restart dabrafenib if LVEF recovers including resolution of symptoms.

* If ECHO does not show LVEF recovery after 2 weeks, repeat ECHO 2 weeks later.

6.3.5.2 Mandatory dose modification and management guideline for hypertension suspected to be related to dabrafenib and/or trametinib treatment

Increases in blood pressure have been observed in subjects receiving trametinib. For adequate monitoring and management of hypertension, all blood pressure assessments should be performed under the following optimal conditions:

- the subject has been seated with back support, ensuring that legs are uncrossed and flat on the floor
- the subject is relaxed comfortably for at least 5 minutes
- restrictive clothing has been removed from the cuff area and the right cuff size has been selected
- the subject's arm is supported so that the middle of the cuff is at heart level
- the subject remains quiet during the measurement.

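### Section 6.3.2 calls LVEF reduction a trametinib-only exception against Table 6-22, and that table has no row for one narrow group of symptomatic subjects

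*Protocol*

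**What the plan says.** The default in Section 6.3.2 for toxicity of the dabrafenib and trametinib combination is that "both treatments should be simultaneously dose reduced, interrupted or discontinued with the exceptions shown below". Among the exceptions needing modification of trametinib alone it names "Left ventricular ejection fraction (LVEF) reduction" and cites Table 6-22. It does not separate asymptomatic from symptomatic cases.

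Table 6-22 in Section 6.3.5.1 has two rows.

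- **Asymptomatic:** "Absolute decrease of >10% in LVEF compared to baseline and ejection fraction below" the institution's LLN. Trametinib is interrupted and, if LVEF recovers, restarted one level lower; dabrafenib continues. The event is reported as an SAE and ECHO is repeated within 2 weeks.
- **Symptomatic:** "Resting LVEF 39-20% or >20% absolute reduction from baseline", or a resting LVEF below 20%. Trametinib is stopped permanently and dabrafenib is interrupted, with this condition for dabrafenib: "Restart dabrafenib if LVEF recovers including resolution of symptoms".

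Table 6-8 marks LVEF with an X for both drugs, where an X "indicates study treatment (s) that may need to be modified".

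Section 6.3.5 sends events special to dabrafenib and/or trametinib to the grade-based Table 6-21. Section 6.3 refers investigators to the Investigator's Brochure and local prescribing information for "the management of other AEs or potential safety-related issues not specifically mentioned in this protocol".

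**The concern.** There are two separate faults in the same dose rule.

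First, the 6.3.2 bullet is true only of the asymptomatic row. For the more serious symptomatic category it says the opposite of the table it cites. A site that relied on the bullet alone would keep dabrafenib going when the table requires it to be interrupted.

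Second, the first row is restricted by its label to subjects without symptoms, and the symptomatic row sets a much higher threshold. A symptomatic subject with a moderate fall meets neither. Such a subject passes to Table 6-21, which acts on grade and not on LVEF. If the event is graded tolerable, the mandatory instruction there is to continue both drugs. A subject with the same LVEF and no symptoms must interrupt trametinib. On that branch, having symptoms leads to less action.

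**Working it through.** **Part 1: the texts side by side**

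| Place | Drugs modified, asymptomatic | Drugs modified, symptomatic |
|---|---|---|
| Section 6.3.2 bullet | trametinib only | trametinib only (no distinction made) |
| Table 6-22 | trametinib only | trametinib and dabrafenib |
| Table 6-8 | both marked | both marked |

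The bullet disagrees with Table 6-22 in the symptomatic column and with the marking in Table 6-8. Table 6-8 does mark some events for trametinib alone (RPED, thromboembolic events), so the double mark for LVEF looks deliberate.

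**Part 2: where no row applies**

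Inputs: the two criteria of Table 6-22, and inclusion criterion 14 (Section 5.2.4), which puts baseline LVEF at or above the institutional LLN. The documents give no number for LLN, so 45, 50 and 55 are assumptions. LVEF is taken in whole numbers.

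- A symptomatic value v below LLN escapes the symptomatic row when v is at least 40 and baseline − v is at most 20. The uncovered range is therefore max(40, baseline − 20) ≤ v ≤ LLN − 1.
- The part where an asymptomatic subject would have to interrupt trametinib also needs baseline − v > 10.

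Example at LLN 50, baseline 60: max(40, 60 − 20) = 40, so 40 to 49 is uncovered. A fall above 10 means v ≤ 49, so the whole range qualifies.

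| Assumed LLN | Baseline | Uncovered symptomatic LVEF | Of which fall above 10 points |
|---|---|---|---|
| 45 | 45, 50 | 40–44 | none |
| 45 | 55, 60 | 40–44 | 40–44 |
| 45 | 65 or above | none | none |
| 50 | 50 | 40–49 | none |
| 50 | 55 | 40–49 | 40–44 |
| 50 | 60 | 40–49 | 40–49 |
| 50 | 65 | 45–49 | 45–49 |
| 50 | 70 or above | none | none |
| 55 | 55 | 40–54 | 40–44 |
| 55 | 60 | 40–54 | 40–49 |
| 55 | 65 | 45–54 | 45–54 |
| 55 | 70 | 50–54 | 50–54 |
| 55 | 75 or above | none | none |

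Baselines are in steps of 5. The symptomatic cell lists a resting LVEF below 20% without a clear connecting word. However that cell is divided, it does not reach values of 40 or more with a fall of 20 points or less.

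**Part 3: what the fallback does in the uncovered range**

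- **Intolerable Grade 2 or Grade 3 (Table 6-21):** both drugs are interrupted and restarted one level lower after recovery. Section 6.3.2 discontinues both "if following an interruption of dabrafenib and trametinib, an AE" does not recover to Grade 1 or baseline within 4 weeks. This is no weaker than the asymptomatic row.
- **Non-infectious myocarditis (Table 6-19):** all three drugs are interrupted at Grade 2, or at Grade 1 that does not improve on symptomatic treatment.
- **Tolerable Grade 1-2, fall of 10 points or less:** both drugs continue. The asymptomatic row would require nothing either, so there is no inversion.
- **Tolerable Grade 1-2, fall above 10 and up to 20 points:** both drugs continue, whereas the asymptomatic row interrupts trametinib. This is the only weaker branch, and it is the last column of the table.

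**The case against.** The bullet in 6.3.2 sits under general instructions, prescribes no action of its own and points to Table 6-22. That table carries the mandatory rule and states the dabrafenib interruption plainly. LVEF is also a genuine exception to modifying the two drugs together, since in the symptomatic row trametinib stops for good while dabrafenib may restart. This stands and limits the risk. It does not make the word limiting the exception to trametinib correct. A reader might infer that the mandatory LVEF rule itself omits dabrafenib; Table 6-22 shows that it does not.

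On the missing row, a reader might infer that these symptomatic subjects have no guidance, or are generally treated less cautiously than asymptomatic ones. The documents do not support that. Table 6-21 and Table 6-19 cover most of the range, the investigator may stop treatment at discretion (Section 6.1.5), and local prescribing information, which is not available here, may add more. Whether a symptomatic fall of this size would be graded tolerable depends on CTCAE v4.03, also not at hand. The one branch remains because, where the event is graded tolerable and is not myocarditis, the written mandatory instruction is to continue both drugs.

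A fair objection to the obvious remedy is that the first row defines recovery by LVEF alone. Extending it unchanged would let trametinib restart in a subject who still has symptoms, while the symptomatic row asks for symptom resolution even before dabrafenib restarts. The remedy has to deal with this.

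**Conclusion.** Both points hold, as a minor correction to a safety rule.

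1. Section 6.3.2 contradicts the symptomatic row of Table 6-22 and the marking in Table 6-8. The table is correct and the pointer is not.
2. Table 6-22 has no row for a symptomatic subject with LVEF of at least 40% but below LLN and a fall of 20 points or less. Less action than in the asymptomatic row follows only for a tolerable Grade 1-2 event with a fall above 10 and up to 20 points.

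The LVEF ranges rest on assumed LLNs of 45 to 55 and on baseline at or above LLN. They show where the table is silent and are not a risk estimate. Section 1.2.2.2.3 names decreased ejection fraction among the commonest reasons for dose reduction and discontinuation with the combination, but gives no frequency for this subgroup. At Amendment 7, 2 + 1 + 88 = 91 patients were still on treatment. Nothing here affects PFS or OS.

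**What to change.** - **Section 6.3.2:** change the trametinib-only bullet to 'Asymptomatic LVEF reduction (Table 6-22)'.
- **Table 6-22:** extend the first-row action (interrupt trametinib, report as SAE, repeat ECHO) to symptomatic subjects with a fall above 10 points and LVEF below LLN who do not meet the symptomatic row. State that this is a minimum and that any stricter action under Table 6-21 or Table 6-19 still applies.
- **Restart:** for these added subjects, require both LVEF recovery and resolution of symptoms before any trametinib restart.

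Symptomatic falls of 10 points or less can stay under Table 6-21.

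The cost is one bullet, one table row and a few sentences, made through an amendment with IRB/IEC approval, plus the extra ECHOs and SAE reports. The clinical downside is that some symptomatic patients, in a number the documents do not give, would have trametinib interrupted and restarted one level lower when they might have continued at full dose. Section 2.3 reports lower efficacy at reduced trametinib doses. That is a reason to set interruption as the minimum and not to make permanent discontinuation the immediate default.
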